# ABBREVIATIONS (Listed alphabetically)

ACOG American College of Obstetrics and Gynecology

AE Adverse Event
BMI Body Mass Index
CRF Case Report Form
DVT Deep Vein Thrombosis

IIQ-7 Incontinence Impact Questionnaire-Short Form

NPV Negative Predictive Value PACU Post-Anesthesia Care Unit

*POD Post-Operative Day* 

PPBC Patient Perception of Bladder Condition

PPV Positive Predictive Value PVR Post-Void Residual SAE Serious Adverse Event

TLH Total Laparoscopic Hysterectomy

[figure not shown]
UTI Urinary Tract Infection

# RESEARCH SCHEMA

#### 1.0 INTRODUCTION

## 1.1. Background

Acute urinary retention is a complication of hysterectomies that can result in bladder over-distension and long term bladder dysfunction. The incidence of acute urinary retention after total laparoscopic hysterectomy (TLH) has been reported to be anywhere between 4% and 34%.  Studies have varied in the method of post-operative bladder challenge and the modality of hysterectomy included. Moreover, most of the published studies are retrospective chart reviews or prospective observational studies, with a lack of randomized controlled trials. Risk factors for urinary retention include type of anesthesia used, how the hysterectomy is performed, use of post-operative narcotics, pre-operative urinary retention, and possibly aggressive bladder dissection.  With the increased trend towards same-day discharge following TLH, urinary retention may cause unnecessary patient distress and a worsened post-operative course. Standardization of post-hysterectomy bladder challenge and identification of risk factors for urinary retention may aid in preventing urinary retention or acute bladder dysfunction.

# 1.2. Investigational Agents

This study does not involve investigational agents.

#### 1.3. Prior Studies

There have been several studies published evaluating acute post-hysterectomy urinary retention and the risk factors associated with having this complication. Several of these studies are not generalizable to our patient population due to their exclusion of patients undergoing same-day discharge. Smorgick et al retrospectively evaluated urinary retention after laparoscopic total and supracervical hysterectomy as well as robotic-assisted laparoscopic hysterectomy over 9 years and found the rate of urinary retention to be 7.3% in total: 10.3% in robotic cases and 4% in laparoscopic cases. The authors concluded that the difference may be attributed to more aggressive bladder dissection in robotic cases. In this study, patients had the Foley catheters removed on post-operative day (POD) 1 as they were admitted overnight. Urinary retention was defined as inability to void by 6 hours or post-void residual (PVR) greater than 100 cc of urine. In another retrospective chart review, Kandadai et al matched patients who underwent hysterectomy and had post-operative urinary retention with patients who underwent hysterectomy and did not have urinary retention in an attempt to determine if analgesic usage contributed to urinary retention. Higher post-operative narcotic doses, pre-operative usage of Tricyclic antidepressants, and pre-operative urinary retention were found to be risk factors for developing urinary retention. However, once again, these patients were admitted overnight and the Foley catheters removed on POD1. Additionally, the authors included vaginal, laparoscopic, and abdominal hysterectomies in the study. 6 Lastly. Won et al sought to report the incidence of bladder dysfunction by prospectively observing 108 women undergoing gynecologic laparoscopic surgery. The incidence of post-operative bladder dysfunction was 19.6%. This sample includes different surgeries and pathologies. Additionally, the Foley catheters were removed on POD1 and patients with same-day discharge were excluded from the study.

Immediate post-operative Foley catheter removal has become more preferable since there is a nationwide effort to discharge patients undergoing laparoscopic hysterectomy on the same day of their surgeries. Additionally, early removal of Foley catheters may improve post-operative

urinary tract infection (UTI) rates. In a study performed by Liang et al comparing urinary outcomes in patients undergoing laparoscopic-assisted vaginal hysterectomy who receive a Foley catheter intra-operatively versus those who do not, 34% of patients were found to have urinary retention in the no catheter group. The patients who had an intra-operative catheter placed underwent removal on POD1 or POD2. Urinary retention occurred in 12% of those who had removal on POD1 and in 10% of those who had removal on POD2. However, the UTI rates were worsened as the Foley catheter remained in place for a longer period of time: 4% in the no catheter group, 6% in the POD1 removal group, and 18% in the POD2 removal group. 4 Ghezzi et al performed a prospective observational study of 233 women undergoing TLH or vaginal hysterectomy evaluating post-operative urinary retention after immediate Foley catheter removal. Post-op voiding dysfunction was defined as failure of voiding after surgery or PVR of 150 mL of greater. In the TLH group, 14.1% had a post-void dysfunction and 7.7% had complete urinary retention. Alessandri et al later reported a prospective randomized controlled trial including vaginal, abdominal, and laparoscopic hysterectomies comparing immediate Foley catheter removal with removal of the catheter 6 hours post-operatively or 12 hours post-operatively. The urinary retention rate was 18.8% for patients in the immediate Foley catheter removal group and 0% for the other groups. However, all of the patients who had urinary retention had undergone vaginal hysterectomy under spinal anesthesia and only 15 patients in the cohort had undergone TLH.

Within the Urogynecology literature, there have been several studies evaluating urinary retention after vaginal hysterectomy and other pelvic floor procedures. These studies have supported the use of a backfill technique post-operatively to prevent post-operative urinary retention. The backfill techniques involves retrograde filling of the bladder via a Foley catheter followed by allowing the patient to void and measuring the PVR. This is different from the autofill techniques which involves immediate removal of Foley catheter post-operatively then allowing the patient to void spontaneously and measuring the PVR. Foster et al randomized 55 patients to receive a backfill-assisted void trial or an autofill void trial after transvaginal surgery resulting in 38.5% of patients going home with a Foley catheter after backfill void trial versus 67.9% going home with a Foley catheter after the autofill void trial (p = 0.02). Additionally, patients remained in the hospital for an average of 199.5 minutes in the backfill void trial group versus 226.6 minutes in the autofill void trial group (p = 0.08). Similarly, Geller et al randomized 60 patients undergoing urogynecologic procedures to obtaining either backfill followed by autofill void trial or autofill followed by backfill. There was a significant difference in the failure rate between the two methods with 62% failing the backfill void trial versus 84% failing the autofill void trial (p =0.001). The backfill method was found to have a sensitivity of 94.4%, a specificity of 58.1%, a positive predictive value (PPV) of 56.7% and a negative predictive value (NPV) of 94.7%. On the other hand, the autofill method was found to have a sensitivity of 100%, a specificity of 25.8%, a PPV of 43.9%, and a NPV of 100%. Moreover, Pulvino et al randomized 65 patients to the backfill technique or the autofill technique reporting the failure rate to be 35% in both groups but noted that there was more complete bladder emptying found in the backfill group, with a voided volume of  $65\% \pm 0.33$  and  $51\% \pm 0.34$ , respectively (p < 0.01).

#### 1.4. Dose Rationale and Risks/Benefits

This is not applicable as no investigational agents will be used.

## 1.5. Hypothesis

Failure of void trial after TLH will be lower after the backfill technique than after the autofill technique.

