#### 2.0 STUDY OBJECTIVES

## 2.1 Primary Objective

The primary objective is to compare the rate of void trial failure after TLH with the backfill technique versus the autofill technique.

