## 2.2 Secondary Objectives

The following variables will also be compared between participants undergoing backfill void trial and autofill void trial:

- Time to discharge: time from arrival to post-anesthesia care unit (PACU) to time of discharge
- Incidence of urinary retention after discharge from hospital
- Incidence of UTI in the first 2 weeks after surgery
- Participants' short term quality of life during the first 2 weeks after surgery
- Participants' satisfaction with the void trials

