#### 7.0 STATISTICAL PLAN

## 7.1 Sample Size Determination

Due to the wide variety of incidence of voiding dysfunction found in the literature, a review of

our own cohort of patients was used to determine the sample size. From May of 2016 to April of 2017, 355 total laparoscopic benign hysterectomies were performed by the minimally invasive gynecology division. Of these, 182 had an autofill void trial and 173 had a backfill void trial. About 28.3% of the backfill void trial patients failed and went home with a catheter while 4.9% of the autofill void trial patients failed and went home with a catheter. Hence, using a 2-indendent group dichotomous power analysis with a power of 80% and a one-sided confidence interval of 95%, we will require 76 patients to be enrolled (38 patients per group). A mid-study analysis will be performed when ½ of the patients are enrolled. To account for patient dropout. We will be enrolling 10% more patients totaling 84 patients for the study.

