#### 8.5 Stopping Rules

An interim analysis of the patient data will be performed when 50% of the patients have completed the study. If a statistically significant proportion of patients are found to have had adverse reactions or serious adverse reactions, the study will halt. If any adverse outcome is fatal, the study will immediately halt and the IRB will be notified. In the case that the study is stopped then the IRB will be notified.

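### Section 1.5 expects fewer failures with backfill, but 7.1 sizes a one-sided comparison, side not named, on local rates that run the other way, so the stated 80% power does not apply to a one-sided test of 1.5

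*Combined protocol and SAP*

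**What the plan says.** Section 1.5 gives the only directional statement in the plan: "Failure of void trial after TLH will be lower after the backfill technique than after the autofill technique". The primary objective in 2.1 is to "compare the rate of void trial failure after TLH with the backfill technique versus the autofill technique", and 3.2 asks only whether the two rates differ.

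Section 7.1 takes its planning rates from the local cohort of May 2016 to April 2017. "Of these, 182 had an autofill void trial and 173 had a backfill void trial", and "About 28.3% of the backfill void trial patients failed and went home with a catheter while 4.9% of the autofill void trial patients failed". The calculation is made "with a power of 80% and a one-sided confidence interval of 95" per cent. It gives 38 per group (76), raised to 84 for dropout. No side is named.

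Section 7.2 compares the proportion with urinary retention by a chi-square test. It gives no alpha, sidedness or continuity correction, and does not name void trial failure. Section 2.2 lists "Incidence of urinary retention after discharge from hospital" as a separate secondary outcome, so the label in 7.2 is loose.

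On interim looks, 7.1 states "A mid-study analysis will be performed when" half the patients are enrolled and gives no purpose. Section 8.5 describes a review at 50% completion: "If a statistically significant proportion of patients are found to have had adverse reactions or serious adverse reactions, the study will halt".

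**The concern.** A one-sided criterion has no meaning until its side is named. The only direction on offer (1.5) is the reverse of the planning rates, and nothing in the plan reconciles the two. The sample size cannot reveal the conflict, because the formula uses only the absolute difference.

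The side decides what the trial may claim. If 1.5 sets it and the 7.1 rates are right, the test will almost surely not reject, and the large difference that 7.1 predicts cannot be declared. If the test is two-sided, the same data give a clear positive result. Participants and study personnel are unblinded (5.8), so the choice should be fixed in writing before the outcome data are examined.

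The two directions have visible origins. Of the three urogynecology trials described in 1.3, two found lower failure with backfill (38.5% v 67.9% leaving with a catheter; 62% v 84% failing) and one found 35% in both groups. Section 1.5 matches that literature. Section 7.1 turns to local data because published incidence varies widely. That makes the reversal understandable but does not resolve it.

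**Working it through.** **Inputs.** From 7.1: backfill p1 = 0.283, autofill p2 = 0.049, d = 0.234, power 80%, one-sided alpha 0.05, 38 per group. The mean rate is 0.166.

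**The cohort rates.** 49/173 = 28.3% and 9/182 = 4.9%, so the printed percentages fit whole counts under the printed labels. This does not prove that the labels are right.

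**Reproducing 38 per group.** n = [z_alpha √(2 × 0.166 × 0.834) + 0.8416 √(0.283 × 0.717 + 0.049 × 0.951)]² / d², with the two roots equal to 0.5262 and 0.4995.

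- One-sided, no correction: (1.645 × 0.5262 + 0.8416 × 0.4995)² / 0.05476 = 30.2, so 31 per group. This does not reproduce 38.
- One-sided, continuity-corrected: (30.2/4) × [1 + √(1 + 4/(30.2 × 0.234))]² = 38.3, so 39.
- Two-sided, no correction: (1.960 × 0.5262 + 0.8416 × 0.4995)² / 0.05476 = 38.5, so 39.
- Two-sided, continuity-corrected: 47.

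The stated 38 is within rounding of two readings: one-sided with correction, or two-sided without. It cannot show which was meant.

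**Power at 38 per group, by normal approximation.** SE under the null = √(2 × 0.166 × 0.834/38) = 0.0854. SE under the alternative = √(0.2495/38) = 0.0810.

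- One-sided, backfill higher: (0.234 − 1.645 × 0.0854)/0.0810 = 1.155, giving 87.6%.
- Two-sided: (0.234 − 1.960 × 0.0854)/0.0810 = 0.823, giving 79.5%.
- One-sided, backfill lower (1.5): (−0.234 − 1.645 × 0.0854)/0.0810 = −4.62, giving about 2 in a million.

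**Exact power**, summing binomial probabilities over all outcomes:

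| Test at 5%, 28.3% v 4.9% | 38 per group | 42 per group |
|---|---|---|
| One-sided for 1.5 (backfill lower), uncorrected | 0.0000037 | 0.0000017 |
| One-sided, backfill higher, uncorrected | 90.0% | 92.6% |
| One-sided, backfill higher, Fisher | 83.1% | 87.1% |
| Two-sided Pearson, uncorrected | 83.8% | 87.5% |
| Two-sided Yates | 71.0% | 76.6% |
| Two-sided Fisher | 74.4% | 80.3% |

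The one-sided Yates test at 38 per group also gives 83.1%.

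**A worked result.** Expected failures are 38 × 0.283 = 10.8 and 38 × 0.049 = 1.9. For 11/38 v 2/38 the pooled rate is 13/76 and z = 2.74. The two-sided p is 0.006; the one-sided p for 1.5 is 0.997.

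**Power for a backfill benefit if the labels stand.** Take autofill at 4.9% and backfill at 0%, the best case possible. With no backfill failures, uncorrected Pearson at 38 per group needs at least 4 autofill failures (z = 2.06; 3 failures give 1.77). The chance of 4 or more in 38 at 4.9% is 11.4%. At 42 per group the same threshold gives 14.9%.

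**Type I error, two-sided Pearson without correction, 38 per group.** Exact 5.2% at a common rate of 16.6%, with a maximum of 5.8% near 9.5%. Yates and Fisher have maxima of 2.9% and 3.0%.

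**The case against.** The best defence is that the objective and endpoint are non-directional, a chi-square test is ordinarily two-sided, and on that reading power is about 80%. A hypothesis may also be a mere expectation. Much of this stands. Section 7.1 is also coherent on its own terms: a one-sided continuity-corrected calculation gives about 38, with exact power of 83.1% if the side is backfill higher. But that side contradicts 1.5, 7.1 does say one-sided, and 7.2 is silent. The two-sided reading is reasonable but is not written down.

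Four stronger readings are tempting, and the documents do not support them.

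- That the plan gives two opposite answers on the side of the test. Only 1.5 states a direction; 7.1 supplies rates and leaves the side open.
- That the trial has no power. The near-zero figure needs both a one-sided test of 1.5 and true 7.1 rates. In that case 1.5 is false, and failing to reject is correct behaviour.
- That the labels in 7.1 are transposed. They may be, and then exact one-sided power for 1.5 would be 90.0%, but nothing in the text shows it.
- That the side will be picked after the results. No passage plans this. Were it done, the exact error rate at a common 16.6% would be 9.8% instead of 4.9%, which is a reason to close the gap and not evidence of intent.

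**Conclusion.** The point holds and should be settled before the primary analysis. Section 1.5 and the planning rates in 7.1 disagree in direction, and the side of a test described as one-sided is undefined. The stated 80% power does not belong to a one-sided test of 1.5, whose rejection probability under the 7.1 rates is effectively zero. The sample size is not in error.

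The consequence is conditional. Under a two-sided 5% test without correction the trial keeps roughly its stated power, but if the labels stand nearly all of that power is for finding backfill worse. All figures assume the 7.1 rates and 38 analysed per group unless 42 is stated. Whether those rates carry the right labels can be settled only from the cohort data.

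**What to change.** 1. Check the cohort data, confirm which method gave 28.3% and which 4.9%, and state the counts in 7.1. If the labels are transposed, correct 7.1. If not, reconcile 1.5 with 7.1, or keep 1.5 as an expectation that is tested two-sided.
2. In 7.1 and 7.2, specify one primary test: two-sided 5% Pearson chi-square without continuity correction, on void trial failure by name.
3. Restate the power in 7.1 as two-sided, 79.5% (normal approximation) or 83.8% (exact) at 38 per group, for the direction that the checked rates show. If the labels stand, add that there is little power to show a backfill benefit: at most 11.4% at 38 per group and 14.9% at 42, with autofill at 4.9%.
4. State whether the mid-study analysis in 7.1 is confined to the safety review in 8.5. The full 5% level holds only if that look does not test void trial failure.

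**Cost.** One data check and wording in 1.5, 7.1 and 7.2; enrolment stays at 84. Power is lower than for a one-sided test in a single named direction (83% to 90% at 38 per group, depending on the correction). Uncorrected Pearson slightly exceeds its nominal level at that size. If the authors prefer Yates or Fisher, they should state that power falls to 71.0% or 74.4% at 38 per group, and is 76.6% or 80.3% only if all 84 are analysed.

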#### 2.0 STUDY OBJECTIVES

## 2.1 Primary Objective

The primary objective is to compare the rate of void trial failure after TLH with the backfill technique versus the autofill technique.

## 2.2 Secondary Objectives

The following variables will also be compared between participants undergoing backfill void trial and autofill void trial:

- Time to discharge: time from arrival to post-anesthesia care unit (PACU) to time of discharge
- Incidence of urinary retention after discharge from hospital
- Incidence of UTI in the first 2 weeks after surgery
- Participants' short term quality of life during the first 2 weeks after surgery
- Participants' satisfaction with the void trials

#### 3.0 STUDY DESIGN

## 3.1 General Design

This will be a randomized control trial. Patients undergoing TLH for benign conditions will be invited and consented to participate in the study prior to the day of their surgery. Each patient will be contacted by one of the study investigators and presented with the study including the risks, benefits, and follow up requirements. She will be given the option to participate and if agrees, she will sign a consent form. All enrolled participants will have a PVR checked and recorded in the clinic using the bladder scanner that is available to us or straight catheterization. The enrolled participants will also be asked to complete the Patient Perception of Bladder Condition (PPBC) and the Incontinence Impact Questionnaire-Short Form (IIQ-7) and the completed forms will be collected by the research team (see attached "Preoperative participant questionnaire"). Each consented participant will be randomized to receive a post-operative backfill void trial or an autofill void trial on the day of her surgery. The participant will not be told of her randomization group pre-operatively; however, the surgical team will be aware of the randomization.

On the surgical day, all enrolled participants will undergo standard registration and preoperative preparation by the staff pre-operative nurse, including placement of intravenous access line and administration of standard preoperative medications. Preoperative medications (unless contraindicated due to allergy or other medication interaction) include single dose prophylactic antibiotics given prior to surgical incision, Tylenol 1,000 mg PO, Dexamethasone 10 mg IV (unless the participant has diabetes), Celebrex 200 mg PO (unless patient has a sulfa allergy, is  $\geq$  65 years old, weighs  $\leq$  50 kg, or has a CCl < 50ml/min), Ondansetron 4 mg IV, and Gabapentin 600 mg PO (300 mg PO if participant is  $\geq$  65 years old) given in the preoperative area.  $^{11,12}$  Participants with a preoperative Caprini score of 5 or greater will also receive Heparin 5000 units

subcutaneously for deep vein thrombosis (DVT) prophylaxis. 13

The participant will be taken to the operating room. Induction, intubation, and anesthesia will be administered according to standard practice by a dedicated group of anesthesia providers. Prior to surgical incision, preoperative prophylactic antibiotics will be administered. The participant will be positioned in the dorsal lithotomy position with the lower extremities in the Allen stirrups bilaterally and the bilateral upper extremities in a tucked position. Surgical sterile preparation and draping will be performed per usual technique. Vaginal antiseptic preparation will be performed with 10% Povidone-Iodine solution. A Foley catheter will be placed prior to the start of the surgical procedure. The hysterectomy will then proceed in the usual manner. After the specimen is removed from the pelvis and the vaginal cuff is closed, a cystoscopy may be performed at the discretion of each surgeon. At this time, the randomization envelope will be opened. Participants who randomize to the backfill void trial will remain with a Foley catheter in place or will have the Foley catheter replaced, in the case that a cystoscopy is performed. Patients who randomize to the autofill void trial will be given a 500 cc bolus of crystalloid by the anesthesia team prior to leaving the operating room. All skin incisions will be closed in a subcuticular fashion and sealed with skin adhesive.

The participant will emerge from anesthesia under routine monitoring and will be transferred to the PACU when meeting appropriate criteria per anesthesia discretion. A staff PACU nurse will care for the participant in the PACU administer narcotic medications as necessary and/or per participant request. Once the participants are awake and meeting criteria for discharge, the patients in the backfill group will undergo a void trial by a PACU nurse or by a doctor if the nurse is unavailable. About 300 mL of fluid will be instilled into the bladder and the Foley will then be removed. The participant will be given up to 1 hour to urinate and the amount urinated will be recorded using a commode specimen collection measurer. The PVR will be measured using a bladder scanner. If the PVR is greater than 100 mL or if the patient is unable to void within the hour, the void trial will be considered "failed" and a Foley catheter will be replaced.

The participants in the autofill void trial group will be allowed to urinate at any time within the first 3 hours after surgery. The amount urinated will be recorded using a commode specimen collection measurer. The PVR will be measured using a bladder scanner. If the PVR is greater than 100 mL, the void trial will be considered "failed" and a Foley catheter will be replaced. We anticipate that most of these patients will void spontaneously within 2 hours of arrival to the PACU. At two hours post-operatively, any patient who cannot void or does not have the urge to void will have a bladder scan. If the patient has more than 300 cc in the bladder, she will be allowed 1 more hour to void. If she cannot, a Foley catheter will be placed and she will be considered to have failed the void trial. If the patient has less than 300 cc in the bladder, another 500 cc of crystalloid bolus will be given and we will await void for another hour. At 3 hours post-operatively, these patients will undergo another bladder scan. Those with greater than 300 cc of urine in the bladder will receive a Foley catheter. Those with less than 300 cc of urine in the bladder will have a backfill void trial by placing the remaining amount of fluid into the bladder for a total volume of 300 cc. The rest of the void trial will be completed as per normal backfill void trial protocol.

The participants who have a replaced Foley catheter will receive education regarding usage of a leg bag and will be discharged home to return to the office the following business day where a

repeat void trial will be performed using the backfill method as previously outlined. If participants are unable to be discharged home, they will be admitted overnight in the hospital with documented rationale. A backfill void trial will then be performed the following day. If participants fail the 2nd void trial, a Foley catheter will be replaced and will remain in place for 1 week, at which time a backfill void trial will be repeated once again in the office. If this void trial is failed as well, participants will be educated about and asked to perform self-catheterization at home and will follow up with Urogynecology.

All participants will be discharged home with uniform medication prescriptions and instructions for usage. The medications will include Ondansetron 4mg PO every 8 hours as needed for nausea/vomiting (quantity 12), Colace 100mg PO twice daily (quantity 60), scheduled Ibuprofen 600mg PO every 6 hours (quantity 30), scheduled Acetaminophen 650mg PO every 6 hours (quantity 30), and Oxycodone 5mg PO every 4 hours as needed for breakthrough pain (quantity 30). These prescriptions are based on recent anesthesia practice guidelines. 14,15

At the post-operative visit 10-14 days after the surgery, the participants will be evaluated and examined in the office. They will be asked to complete a questionnaire which includes the IIQ-7, the PPBC, and a void trial satisfaction question (see attached "post-operative participant questionnaire"). Participants will also be asked if they obtained a Foley catheter outside of the hospital at any urgent care centers, other doctors' offices, or emergency rooms. Additionally, participants will be asked if they have any urinary problems including dysuria, hematuria, frequency, hesitancy, urgency, or incomplete emptying. If any urinary complaints exist, participants will be asked to provide a urine sample for testing by urinalysis and urine culture. Participants will be treated per physician preference. After treatment, participation in the study will be considered completed.

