## 3.2 Primary Study Endpoints

The primary endpoint of this study will be to determine if the rate of void trial failure after TLH is different after the autofill method versus the backfill method.

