## 5.2 Treatment Regimen

The interventions were be performed post-operatively in the PACU. See the following sections for more detail as to how the study interventions will be carried out.

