
# 6.4 Post-op Day 1 Visit (applicable only if 1st void trial fails)

Participants who fail the post-hysterectomy void trial (their 1st void trial) will be scheduled for a nurse visit on POD1, where a repeat void trial will be performed using the backfill method as

previously outlined. If the participant was admitted to the hospital, a backfill void trial will then be performed the following day in the hospital. If participants fail the 2nd void trial, a Foley catheter will be replaced and will remain in place for 1 week.

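### Does finishing some autofill void trials with a backfill top-up undermine the primary comparison?

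*Combined protocol and SAP*

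**What the plan says.** Section 3.1 of the combined protocol and SAP sets out the autofill pathway, and sections 5.4 and 6.3 repeat it. A woman who has not voided at 2 hours is scanned. If she holds less than 300 cc, she gets a second crystalloid bolus and another hour. At 3 hours she is scanned again, and there are two branches:

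- Over the threshold: "Those with greater than 300 cc of urine in the bladder will receive a Foley catheter".
- Under it: "Those with less than 300 cc of urine in the bladder will have a backfill void trial", filled to a total of 300 cc, after which "The rest of the void trial will be completed as per normal backfill void trial protocol".

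The protocol does not expect many women to get this far: "We anticipate that most of these patients will void spontaneously within 2 hours of arrival to the PACU".

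The primary objective (2.1) is to "compare the rate of void trial failure after TLH with the backfill technique versus the autofill technique", and the endpoint (3.2) is to "determine if the rate of void trial failure after TLH is different after the autofill method versus the backfill method". Section 7.2 gives a chi-square test on the proportion with urinary retention. Section 7.3 includes all treated patients. None of these four sections mentions the top-up.

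Two other passages bear on the reading. Section 5.2 sends the reader onward for the content of the interventions: "See the following sections for more detail as to how the study interventions will be carried out". Section 6.4 gives the repeat trial on the first post-operative day to "Participants who fail the post-hysterectomy void trial", and calls that post-hysterectomy trial the first.

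**The concern.** Section 1.3 describes the two techniques by contrast: backfill is retrograde filling through the catheter, and autofill is catheter removal followed by spontaneous voiding. On that description, a topped-up woman in the autofill arm is tested by the comparator technique, yet her result counts for autofill. The objective and endpoint speak of technique and method, not of pathways. A reader could take the result as a pure contrast of spontaneous voiding with backfill, and credit autofill with passes that the top-up produced.

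The counts are small enough for this to show. At the planning rate, only about two autofill failures are expected among 38 women, so two topped-up women who pass would equal that whole count.

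There is also a wording gap. Women over the threshold at the 3-hour scan are catheterised, but that sentence does not call them failures, although the sentence for women already over it at 2 hours does.

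**Working it through.** **Inputs from section 7.1:** failure 28.3% (backfill) and 4.9% (autofill) in the centre's own cohort; 38 per group; 80% power; one-sided 5%. **Assumed, because the documents give no figure:** the share c of autofill women who reach the top-up, and a top-up pass rate equal to the cohort backfill pass rate, 1 − 0.283 = 0.717.

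**1. The plan's own figure.** The usual formula for two proportions, pooled variance under the null, one-sided 5%, 80% power, gives 30.2 per group. With continuity correction it gives 38.3, or 39 when rounded up, which agrees with the stated 38 to within one patient. 76 × 1.10 = 83.6, the stated 84. Stating which regimen is compared does not alter this calculation.

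**2. Is each patient's outcome determined?**

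- *Topped-up woman.* Section 6.4 recognises one post-hysterectomy trial as the first and places the second at the next-day visit. The top-up happens in the PACU, before that visit, so it belongs to the first trial and she takes its result. No competing coding rule appears.
- *Over the threshold at 3 hours.* She is catheterised. Section 3.1 sends women with a replaced catheter to a repeat trial, and section 6.4 gives that repeat trial to women who failed the first. Her status is failure; only the word is missing.
- *Planning rates.* Section 7.1 counts women who failed and went home with a catheter, which is an end-of-pathway result of the same kind.

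**3. How far would recoding move the result?** Expected failures are 38 × 0.049 = 1.9 (autofill) and 38 × 0.283 = 10.8 (backfill). Treat 4.9% as the pathway rate and count topped-up women who pass as not passed by spontaneous voiding. The autofill rate becomes 4.9% + 71.7% × c.

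| c | Women of 38 | Autofill rate | 28.3% minus rate | Implied failure rate in the others |
|---|---|---|---|---|
| 0 | 0 | 4.9% | 23.4 points | 4.9% |
| 2% | 0.8 | 6.3% | 22.0 | 4.4% |
| 5% | 1.9 | 8.5% | 19.8 | 3.7% |
| 10% | 3.8 | 12.1% | 16.2 | 2.3% |

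The last column is (0.049 − 0.283c)/(1 − c). It limits how large c can be. At c = 15% it is (0.049 − 0.0425)/0.85 = 0.8%, and above 0.049/0.283 = 17.3% it is negative. Large shares therefore do not fit the inputs.

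With 11/38 backfill failures, the risk differences and Newcombe 95% intervals are:

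- 2/38 autofill failures: 23.7 points (6.7 to 39.9)
- 4/38 (two top-up passes recoded): 18.4 (0.3 to 35.5)
- 5/38 (three recoded): 15.8 (−2.7 to 33.2)

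These describe the recoded quantity, not the primary comparison.

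**4. Does the top-up weaken the primary test?** If 4.9% already includes such women, power is unchanged. If instead 4.9% applies only to the rest and topped-up women fail at 28.3%, the pathway rate is 4.9% × (1 − c) + 28.3% × c. That is 6.1% at c = 5% and 7.2% at c = 10%. One-sided power at 38 per group (normal approximation, uncorrected) goes from 87.6% to 83% and 78%. The documents do not say which case applies. Either way this is uncertainty in a planning rate, and a coding rule would not change it.

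**The case for a change.** The strongest case for a change is that analysing by assigned arm protects validity but does not settle interpretation. The stated question is about technique, section 7.3 defines who is treated rather than the group in which she is analysed, and three recoded passes would take the interval across zero. A coding rule chosen after outcomes are seen would be open to challenge. On this view, section 3.2 should name the pathway reading and section 7.2 should add a supportive analysis counting topped-up women as not passed by spontaneous voiding.

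Part of this stands. The plan does not call the comparison one of regimens, and a report that presented it as an isolated test of spontaneous voiding would overreach. The number of top-ups and their results belong in the report. Section 6.7 has no separate row for the 3-hour scan or the top-up, but its row for the first void trial can include them. The case report form is not in the documents, so nothing can be inferred about what it records.

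The rest does not require a change. The description in section 1.3 is literature background; the arm is defined in section 5.4, which includes the top-up. It is neither a crossover nor a deviation. The supportive analysis would turn passes into non-passes in the autofill arm only, so it can only move the result against autofill. It also counts an under-filled bladder as not passing, which is a different outcome from the endpoint. The 71.7% pass rate comes from unselected backfill patients and is applied to women who have not voided for 3 hours; nothing in the documents supports that transfer.

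**Conclusion.** No change to the plan follows. Followed as written, it gives a valid randomised comparison of two fully described regimens, with the outcome of topped-up women and of those catheterised at 3 hours fixed by sections 3.1 and 6.4. What is missing is explicit wording, and an analyst would supply it the same way: the final result on the day of surgery under the assigned regimen.

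The difference between regimens and technique is about 1 to 7 points for shares of 2% to 10% (23.4 − 22.0 = 1.4; 23.4 − 16.2 = 7.2). This rests on an assumed share, an assumed 71.7% pass rate, and 4.9% being the pathway rate. The true share may be small, since the step requires no void and a low volume at two scans with a bolus between them. The conclusion should be worded as a comparison of the two regimens, with a descriptive count of top-ups; the recoded analysis is optional.
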